Benchmarks for success: Although it is difficult to precisely predict the effect of cooling on ulcer incidence during the study in these two groups, we view a 50% reduction in the incidence of a leg ulcer in the cooling pack group compared to placebo 7,9.

Impact on pain, physical activity and quality of life – pain will be assessed using a visual analog scale (0.99 interrater reliability) 63 and the Brief Pain Inventory (Cronbach's 0.88) 64, physical activity with an accelerometer (Basis Smart Watch, Basis Science, Inc., San Francisco), a user-friendly activity monitor <http://www.mybasis.com/> and International Physical Activity Questionnaire (IPAQ) (pooled Spearman R 0.81) 65, and quality of life with the VEINES QOL/sym Questionnaire (internal consistency 0.87; test-retest reliability 0.86) 66, the Neuropathic Pain Questionnaire (NPQ) (internal consistency 0.82), the Geriatric Depression Scale, and the SF-12 Health Survey. The VEINES will be administered to the VLU participant population and the NPQ to the DFU participant population. While we recognize that wrist monitors may not be the most accurate in terms of energy expenditure, we are working with an atypical population where hip or bicep-type accelerometer sensors found in (i.e., Bodymedia Fit, and Fitbit Zip), may not be feasible. Thus, we have selected a wrist accelerometer based on data that suggest this design may be better suited for chronic populations; results revealed acceptable agreement between the Basis watch and indirect calorimetry found in hip sensors 67. Basis captures resting movements, is less easy to misplace/lose than hip accelerometers, has multiple-sized wrist bands, and numerous programmability options. These three outcomes will be assessed at baseline, and months 1, 3 and 6. **Benchmarks for success:** Compared to the placebo group, the cooling pack group will have lower pain scores (lower VAS and IPAQ scores), increased physical activity (e.g., more steps taken and participates more frequently in activities, and higher ratings on the SF-12), and improved quality of life (higher ratings on VEINES or NPQ, and GDS).

Analysis plan for Aim 1

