Baseline visit - demographic information (i.e., age, race, gender, co-morbid conditions, body mass index, number of previous ulcers, length of healing time, location, medications taken) and questionnaires on pain, physical activity and quality of life will be collected, affected leg or foot skin at the site of the newly healed ulcer to identify the “hot spot” will be imaged, procedural instructions for using the accelerometer given, protocol for self monitoring of temperature and self management of temperature elevation will be shown via DVD and written instructions given, and a test will be administered to assess understanding. Similar to our other studies, we will produce a YouTube video and take-home DVD of these instructions for standardization. Supplies include: thermometer, pack and freezer bag (given by Research Nexus staff after the research assistant has completed all study procedures) to be kept in freezer at all times except during treatment, a freezer thermometer to ensure temperatures are kept at 0°F, skin marker, study logs and clipboard with attached pen for recording daily temperatures/maintenance and bolus cooling (times, dates)/freezer temperature, and timer (for 30 minutes of cooling). Baseline questionnaires to be administered include: VAS, BPI, IPAQ, SF-12, GDS, and the VEINES QoL or NPQ (as applicable).

Visit 1 – (month 1) - the daily month 1 temperature readings taken over 28 – 31 days (depending on the month) with the thermometer will be downloaded using a software program and averaged to establish the mean skin temperature. These data will be recorded in REDCap. The infrared thermometer will be programmed to sound an alarm when the readings are 2°F above the mean. Also at this visit the skin site will be imaged with the infrared camera and uploaded for comparison against the baseline reading. Data will also be uploaded from the accelerometer to assess physical activity. Any changes in demographics such as taking new medications will be evaluated, and the pain scales will be administered. Process measures will be collected including ease of use of thermometer, problems with study procedures, and fidelity to self-monitoring assessed (e.g., through downloaded temperature readings). Visit 1 questionnaires to be administered include: VAS, BPI, IPAQ, and the VEINES QoL or NPQ (as applicable).

Visit 2 – (month 3) – the daily months 2 and 3 temperature measurements and accelerometer
Version 10.0 07/23/18

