information will be downloaded, the skin site imaged, and demographic (i.e., changes in co-morbid conditions, new medications taken) and pain questionnaires administered. Process measures will be collected. Visit 2 questionnaires to be administered include: VAS, BPI, IPAQ, and the VEINES Qol or NPQ (as applicable).

Visit 3 – (month 6 final visit) – the daily months 4 – 6 temperature measurements and accelerometer information will be downloaded, the skin site imaged, demographic, pain and quality of life questionnaires administered. Process measures will be collected. Visit 3 questionnaires to be administered include: VAS, BPI, IPAQ, SF-12, GDS, and the VEINES Qol or NPQ (as applicable). During this final visit, an exit satisfaction survey interview will be conducted to ascertain information about overall feasibility, problems encountered, satisfaction, recommendations for changes to procedures, likelihood of maintaining/sustaining.

Ongoing supportive phone calls: Calls will be made to both groups 24 hours after the start of the study, weekly during weeks 1 – 4, and then monthly by research assistants. We will provide reinforcement of study procedures, solicit information about problems encountered, adherence, side effects, and leg temperatures and answer any questions (§Table 4).

Study staff: We will elicit feedback using a rating scale we have developed for our ongoing R01 that assesses the perceptions of staff, their beliefs regarding the sustainability of the intervention, likelihood of implementation into practice, and dissemination potential.

Relevant literature in support of or in disagreement with the potential results on pain:

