Human participants will be invited to participate in this study to test the preventive cooling intervention applied to newly healed skin of healed venous leg and diabetic foot ulcers. The goal is to prevent leg or foot ulcer recurrence. We will invite potentially eligible individuals to participate after screening them for adequate blood flow using an ankle brachial index (ABI). The healed area will be imaged with an infrared camera to capture a skin temperature "map" of the affected skin. Participants will then self-monitor the skin temperature of the highest area or "hot spot" with an infrared thermometer daily at home and apply a cooling or placebo pack (self-management) to the affected area for 30 minutes, three times each week. If an elevation is noted above baseline, they will apply the pack using a bolus-dosing regimen for 5 consecutive days. The study will be conducted over 6 months and require 4 visits including baseline, then months 1, 3 and 6. At each study visit, participants will complete the Geriatric Depression Scale (GDS) instrument. Participants with Total GDS scores greater than "5" (suggestive of depression) will be provided with 3 referrals to local area mental health care providers by study staff. Study staff will document the referral process in the participant's REDCap study eCRF. Process and safety monitoring data will be ascertained during weekly phone calls during the first month, then monthly. We will also inquire about safety and tolerability during phone calls and during study visits to include adherence (fidelity), side effects, comfort, and any other problems noted during the study. Both groups (cooling pack and placebo), during the baseline visit after eligibility is determined, will watch a DVD for the sole purpose of standardizing the instructions they receive. Participants will then be quizzed on their knowledge of the study procedures, and will demonstrate self-monitoring with the thermometer, self-managing skin temperature elevation with the pack, when to report problems, and the frequency of return visits.

Targeted/Planned Enrollment Table

Total Planned Enrollment: 180

TARGETED/PLANNED ENROLLMENT: Number of Subjects			
Ethnic Category	Sex/Gender		
	Females	Males	Total
Hispanic or Latino	1	1	2
Not Hispanic or Latino	107	71	178
Ethnic Category: Total of All Subjects*	180		
Racial Categories			
American Indian/Alaska Native	0	0	0
Asian	0	0	0
Native Hawaiian or Other Pacific Islander	0	0	0

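### The Geriatric Depression Scale and its referral rule are promised at all four visits, but the visit questionnaire lists leave the scale out at months 1 and 3

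*Combined protocol and SAP*

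**What the plan says.** **Section E.1, Risks to the Subjects.** There are four visits: baseline, then months 1, 3 and 6. On the GDS the text is explicit: "At each study visit, participants will complete the Geriatric Depression Scale (GDS) instrument". Participants whose total exceeds 5 "will be provided with 3 referrals to local area mental health care providers by study staff", and staff record the referral in the participant's electronic case report form.

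**Section D.9, Data collection time points.** The same four visits each have a list:

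- Baseline: "Baseline questionnaires to be administered include: VAS, BPI, IPAQ, SF-12, GDS, and the VEINES QoL or NPQ (as applicable").
- Month 1: "Visit 1 questionnaires to be administered include: VAS, BPI, IPAQ, and the VEINES QoL or NPQ (as applicable").
- Month 3: "Visit 2 questionnaires to be administered include: VAS, BPI, IPAQ, and the VEINES Qol or NPQ (as applicable").
- Month 6: "Visit 3 questionnaires to be administered include: VAS, BPI, IPAQ, SF-12, GDS, and the VEINES Qol or NPQ (as applicable").

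**Section D.9, Outcome measures for Aim 1.** The quality of life instruments are VEINES (venous participants) or NPQ (diabetic foot participants), with "the Geriatric Depression Scale, and the SF-12 Health Survey". Pain, physical activity and quality of life, as outcomes, are timed at baseline and months 1, 3 and 6.

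**The concern.** The every-visit statement and the referral rule stand in the Protection of Human Subjects section, so they describe a safeguard as well as a measurement. The lists in D.9 are what a research assistant would naturally follow on the day. Where the two differ, the safeguard may not be delivered as described.

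Under the lists, a participant whose mood worsens after baseline would have no GDS, and so no GDS-triggered referral, until the final visit. A participant who leaves before month 6 would have no GDS after baseline at all. The Data and Safety Monitoring Plan, Section C.4, also makes protocol deviations reportable, so staff need to know which schedule is the protocol.

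**Working it through.** The plan gives no figure to reproduce. The check sets the two schedules side by side and counts.

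| Visit | GDS under E.1 | GDS in D.9 list | SF-12 in D.9 list |
|---|---|---|---|
| Baseline | yes | yes | yes |
| Month 1 | yes | no | no |
| Month 3 | yes | no | no |
| Month 6 | yes | yes | yes |

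**Screens per participant who completes.** E.1: 4. Lists: 2. Difference: 4 − 2 = 2. After baseline: 3 against 1.

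**Longest gap between screens.** E.1: the gaps are 1, 2 and 3 months, so the maximum is 3. Lists: 6 − 0 = 6 months.

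**Screens lost by time of exit.**
- Before month 1: 0 promised, 0 listed; none lost.
- Between months 1 and 3: 1 promised, 0 listed; one lost.
- Between months 3 and 6: 2 promised, 0 listed; two lost.
- Completers: 3 promised after baseline, 1 listed; two lost.

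**Total across the trial.** With the planned enrolment of 180 (Section E.1) and no attrition, 3 × 180 = 540 follow-up screens are promised and 1 × 180 = 180 are listed, a difference of 360. With the 240 randomized in Section D.8, the difference is 2 × 240 = 480.

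Section D.6 expects attrition of about 25% but gives no exit times. Assume that this figure covers all exits. If every leaver goes before month 1, the loss is 2 × 0.75 × 180 = 270. If every leaver goes after month 3, it is 360. The range is therefore 270 to 360 for 180 participants. For 240 it is 2 × 0.75 × 240 = 360 up to 480. Withdrawals for a new ulcer on top of the 25% would bring the lower ends down. These are counts of questionnaires. The documents do not say what share would score above 5, so no number of missed referrals can be given.

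**The case against.** **The lists may not be exhaustive.** They are introduced as what the questionnaires include. This carries little weight. The four lists share one pattern, and the GDS and SF-12 are the only instruments that appear at baseline and month 6 and are absent in between. A reader would take that as intended.

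**The omission may be deliberate.** The visit narratives mention pain instruments at months 1 and 3, and at month 6 "pain and quality of life questionnaires administered". On that reading the sentence in E.1 is the outlier. This is possible, but the narratives do not track the lists closely: VEINES or NPQ and the IPAQ are listed at every visit. If the omission is deliberate, E.1 is wrong and still needs correcting.

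**The safety consequence is conditional and modest.** This stands. The case report forms are not in the document, so actual practice is unknown. The trial is classed as minimum risk, and baseline screening with referral appears in both texts. Phone calls, adverse event questions at every contact and a 24-hour reporting line continue. None of these applies the GDS threshold, however.

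**A reader might infer a wider failure:** that the SF-12 is also missing from visits where it was promised, or that the planned quality of life comparisons at months 1 and 3 lack data. The documents do not support this. E.1 makes no statement about the SF-12, and no section expressly schedules it at month 1 or 3. The timing sentence in D.9 refers to the three outcomes, not to each instrument, and VEINES or NPQ still covers quality of life at those visits. The analysis plan does compare quality of life totals at 1, 3 and 6 months, but its worked adjusted model uses change from baseline to 6 months, which two SF-12 measurements support. The quality of life effect size in D.8 rests on VEINES, which is listed at all four visits.

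**Conclusion.** The conflict over GDS timing is real and nothing else in the protocol resolves it. If staff follow the lists, two of the four promised screens are skipped, the referral rule cannot act between baseline and month 6, and the longest gap doubles from 3 to 6 months. That is a specific gap in a participant safeguard and worth correcting.

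The conclusion that the texts disagree rests on the wording alone. The consequence rests on the assumption that the lists, rather than E.1, drive what is done at visits. The total of 360 skipped questionnaires (480 with 240 participants) is an upper bound and should not be read as a count of missed depression. The point does not touch the ulcer recurrence analysis, the sample size or the power. For the SF-12, only a clarifying sentence is needed.

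**What to change.** Add the GDS to the Visit 1 (month 1) and Visit 2 (month 3) lists in Section D.9. State there that the GDS is scored during the visit and that the above-5 referral is applied and recorded before the participant leaves. Check that the electronic case report forms carry the GDS at all four visits.

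In the D.9 outcome measures and the analysis plan for Aim 1, state that SF-12 change is assessed from baseline to month 6 only.

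The cost is one short questionnaire at each of two visits that already administer questionnaires, slightly more participant burden, and some additional referral documentation. If the sponsor intends only two GDS administrations, E.1 should be limited to baseline and month 6, and the analysis plan should say that GDS change is assessed at month 6. That needs only wording, but it gives up two screens that the human subjects section now promises.

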Although vascular disorders appear as early as the first decade of life, venous leg and diabetic ulcers rarely occur in children, and therefore, children under 18 will not be recruited.

E.1.b. Sources of Materials. Materials obtained from the human participants include demographic data, circulation status (ABI), skin temperature mapping, physical activity with an accelerometer, and questionnaires that will be recorded in an electronic documentation web-based data management system (REDCap), from laptop/tablet computers. In the event of a failure to access REDCap, paper source documents have been created. All paper data will then be entered into the system as soon as possible. These documents will then be stored in the PIs office in a locked file. Demographic data about gender, age, ethnicity and pertinent medical history will be collected from the participants by self-report in order to describe the sample. These data will be used for research purposes only. REDCap is password protected and will only be accessible to select members of the research team, including the PI, project director and biostatistician.

E.1c. Potential Risks. After informed consent is obtained, screening data collected, and eligibility established, 180 individuals will be enrolled. Collecting data poses a minimal risk to confidentiality. All enrolled participants will be given instructions about the study procedures both verbally and in writing. The PI, project director, and biostatistician will have access to the data for analysis. If paper documents are necessary in the event of REDCap network failure, documents such as source documents, consent and HIPAA forms, questionnaires, and interview data will be stored in a locked file in the PIs office. The PI and project director will be the only study personnel with access to the paper files. There is minimal risk to the participants, as the cooling intervention has had no side effects noted in our ongoing study. All procedures are non-invasive and non-pharmacological. There may be some minor inconveniences to participants as the tests will take about 1 hour and they will have to remain in the supine position for approximately 20 minutes during the study to ascertain the ABI. Every effort will be made to make the

participants comfortable and provide privacy.

There are no known alternative treatments for this proposed intervention.

E.2. ADEQUACY OF PROTECTION AGAINST RISKS

E.2.a. Recruitment and Informed Consent The recruitment plan includes referrals from our well-established clinical sites that have been actively involved in our previous research studies. We have access to a diverse participant pool from rural settings from which to recruit. We will recruit underserved and underrepresented minorities. We have developed an extensive recruitment plan for our previous studies and have refined several strategies to ensure our enrollment targets are met for this study. Based on our recruitment metrics from our ongoing R01 and [name] experience as the director of recruitment of MUSCs CTSA, we expect to enroll 1 subject for every 5 approached and screened (#1 reason for not enrolling is an abnormal ankle brachial index). The goal is to enroll ~6 subjects per month for 3 1/2 years, accounting for an expected attrition rate of ~25% (nature of the chronically-ill population with frequent hospital admissions). Our recruitment plan includes referrals from centers and practices (50% of participant will be referred), however we anticipate using other recruitment methods that we have found particularly successful including television, radio and billboard advertisements, use of our CTSA's SCResearch.org website, and our community based participatory research advisory groups. We have budgeted for these strategies accordingly. There is a need to incentivize center and practice referrals and to that end, we will provide \$20 for every enrolled participant in the form of a "credit" gift card that can be used for whatever purposes deemed appropriate by the practice. **Retention:** We also have implemented a very successful contingency management approach for retention at one of our study sites (a drawing from a bowl at each visit with the opportunity to win from \$1 to \$100). The attrition rate for this site is ~17% compared to 30% (average of other sites' attrition rates).

We will provide packets of information about the study to referral sources that will provide information about calling a designated number to learn more about the study. Our study team will contact potentially eligible participants, discuss study details, and if interest is expressed in participating in the study, and the baseline study visit appointment will be arranged. The study will be conducted at the Research Nexus (CTSA) at MUSC, the Spartanburg Wound and Healing Center, and at East Carolina University. We will visit the referral sites on a regular basis to evaluate participant identification strategies and to assess the potential for selection bias. IRB approved flyers and marketing materials will be available at these sites, and disseminated through a network of local area provider clinics, and at the Charleston Veteran's Affairs Medical Center (VAMC-534). Participants will receive \$250 compensation for participation: \$25 first visit screening; \$50 baseline visit; \$50 for visits 2 and 3, \$75 for visit 4.

The informed consent and Health Insurance Portability and Accountability Act (HIPAA) forms assure confidentiality of all information obtained during the study. Participants have the right to withdraw from the study at any time without any effect on the care they will receive in the future. Informed consent, approved by the Institutional Review Committee (IRB), will be obtained by the research nurses and signed by the patient indicating willingness to participate in the study. All study personnel have successfully completed the CITI Course in The Protection of Human Research Participants and Clinical Research Training through the National Institutes of Health. Certificates are on file at the IRB. A document, required by the IRB, will have recorded information regarding the time and date of consent, participant screening time and date, participant enrollment time and date, and study completion time and date. The research assistant obtaining this information will sign after each entry. To determine participant understanding of the nature of the study, the research assistant will assess understanding by asking the following questions (participants must be able to answer "yes" to all):

- briefly describe the purpose of the study.
- report the purpose of taking skin temperature and using the pack.
- describe the expectations for the study.
- demonstrate how to operate the thermometer and accelerometer.
- demonstrate how to apply pack.
- state that the study lasts for six months.
- report that they will attend a three additional study visits during the six-month intervention trial.
- state that they agree to wear compression stockings and/or diabetic footwear

E.2.b. Protection Against Risk

In the event of an unexpected medical or other event, the patient will be instructed to contact the research assistant. Based on the experience of the PI, it is anticipated that the risk of adverse events (AEs) will be acceptably very low. In the event of an AE, it will be recorded, the PI notified, and submitted to the IRB according to institutional procedures. All AEs will be reviewed by the PI and project director. Maximum efforts will be undertaken to ensure the safety of all participants. Study personnel will receive extensive training and orientation on procedures and protocols. Participants will be instructed on how to access the PI or research assistants in the event of a study-related question. In the event of study-related illness or injury, participants will be instructed on how to access health care. Although we do not anticipate any problems, we will address any that might arise such as reports of uncomfortable sensations in the leg or foot during or after pack application or the development of new leg or foot ulcers. This information will be recorded and if deemed as an AE by the research team, institutional procedures will be followed for reporting them. An order from the primary health provider is not required for participation in this study as there is oversight by the study MD, [name] and [name] at the Research Nexus. The accelerometer used to measure activity is small and does not pose any problems with being anchored to clothing.

Safety and side effects. There has been considerable attention given to the selection the cooling pack used in this study. We have refined the protocol, as noted in the overview to cool less surface area, targeting the “hot spot” only. We have taken precautions to use a cooling approach that does not aggressively or quickly reduce skin temperature, rather, the material used in the gel wrap does not freeze into a solid state, thus does not rapidly pull heat from the tissue. It is also enclosed in two polyethylene covers to prevent sticking to the skin. The pack will be anchored with a stretchy net “tubing” that can be pulled onto the foot or lower leg. In the event that the participant falls asleep or forgets to remove the pack during the procedure, the pack does not continue to transfer heat from the skin after approximately 15 minutes. There are minimal risks for injury to the skin using the methods of measuring skin temperature with the thermometer.

E.3. POTENTIAL BENEFITS OF THE PROPOSED RESEARCH TO THE SUBJECTS AND OTHERS

Conditioning the lower legs may improve some of the symptoms associated with leg ulcers such as pain and discomfort. The use of the accelerometer and Smartphone for providing patient feedback and giving reminders, involves patients in their own care and may help them feel empowered to reduce the negative effects of having a chronic disease. The long-term effects of having better conditioned lower legs may provide protection for ulcer relapse in high risk groups of patients, and could lead to greater health improvements if the potential to engage in more aerobic forms of physical activity is reached. This study involves minimal risk as a non- invasive study. The benefits outweigh the slight inconvenience to the patient in terms of anticipated new knowledge gained from the study.

E.4. IMPORTANCE OF THE KNOWLEDGE TO BE GAINED

This study will provide valuable information to test an intervention that could potentially improve outcomes in participants vulnerable to lower leg and foot ulcer recurrence. The science of using infrared technology has led to advancements in ulcer prevention measures for both venous and foot ulcer participants. Non-pharmacotherapeutics (i.e., sequential compression devices, temperature mapping) have contributed to significant improvements in self-management of venous disease and diabetic foot complications. However, there has been little attention directed toward ulcer prevention strategies for chronic ulcer recurrence that incorporate an intervention that includes patient self-managing of signals of tissue damage such as inflammation. We propose to “re-invent” an old, yet effective cooling method that has negated the effects of inflammation associated with acute tissue injuries. This simple, inexpensive method, using a small pack, could improve current guideline-guided usual care by focusing on skin temperature, using maintenance cooling, and then bolus doses for elevations noted outside of the baseline “normal” temperature. This approach is novel in that it targets newly healed chronic ulcers. Finally, if the intervention is valid and reliable in this high-risk ulcer population, we envision our strategy will become a mainstream practice standard for the prevention of ulcer recurrence in the future.

E.5. SUBJECT SAFETY AND MINIMIZING RISKS (Data and Safety Monitoring Plan)

The study has a well-developed DSMP that has undergone NIH/NINR SRG review and approval. This plan is contained below:

Application number: 1 R01 NR015647-01

Project title: Monitoring and managing newly healed chronic leg and foot ulcer skin temperature: a cooling intervention (MUSTCOOL) to prevent ulcer recurrence

Principal investigator: [name], RN

DATA SAFETY AND MONITORING PLAN (DSMP)

SECTION A. Monitoring Entity

Considering the study rationale, population, procedures, and the risk:benefit profile, the overall risk level for participation in this study is classified as: **Minimum Risk**. The study will employ the use of a Data Safety Monitoring Committee (DSMC) that will meet semi-annually across all years of the study. The DSMC members are charged with reviewing safety and trial progress and providing recommendations to the PI and MUSC IRB with respect to study continuation modification, and termination.

1) Data Safety Monitoring Committee (DSMC)

